6.1 Dose, Regimen, and Treatment Period

The 0.3% or 1% formulation or the vehicle of OPA-15406 ointment will be administered twice daily (approximately 12 hours apart between morning and night administration) for 8 weeks.

The amount of IMP (g) per dose is calculated as follows.

- 1) The subject's BSA (m^2) will be calculated based on height and body weight at the screening examination, using the following equation.

$$\text{BSA (m}^2\text{)} = \sqrt{\frac{\text{Ht (cm)} \times \text{Wt (kg)}}{3600}}$$

BSA = body surface area;
Ht = height; Wt = body weight
(Mosteller 1987)⁴

- 2) Based on the subject's BSA (m²), the amount of administration (g) for 1% of BSA will be selected from [Table 6.1-1](#).
- 3) The treatment area will be specified (see [6.2 "Treatment Area"](#)).
- 4) The amount of IMP (g) per dose will be calculated as "the amount of administration for 1% of BSA (g)" × "treatment area (%)."

Table 6.1-1 Amount of Administration (g) for 1% of BSA Based on the Subjects' BSA (m²)					
BSA (m²)	<1.0	≥1.0 and <1.3	≥1.3 and <1.6	≥1.6 and <1.9	≥1.9
Amount of administration (g) for 1% of BSA	0.1	0.15	0.2	0.25	0.3

[Rationale for dose, regimen, and treatment period]

[Regimen]

Skin preparations are always exposed to opportunities of being removed after administration to the skin, such opportunities as washing the face, bathing, adhesion to clothing, or sweating resulting in dilution. To be sure that effective concentration on the skin is maintained, it is desirable that the IMP be administered multiple times a day. In consideration of the fact that people generally wash their face and hands after getting up and when bathing at night, twice daily administration is considered highly convenient for patients, and it may contribute to achieving the best adherence. Therefore, twice-daily administration is employed.

[Dose]

In the phase 1 trial in AD patients in the US (271-12-204), the efficacy of OPA-15406 was suggested in the 0.3% and 1% formulations out of the 0.3%, 1%, and 3% formulations tested. In the phase 2 trial outside Japan (271-12-205), the efficacy of OPA-15406 was investigated by selecting the 0.3% and 1% formulations. The results showed that the 1% formulation had a significantly higher efficacy in the primary efficacy endpoint compared to the vehicle, and the 0.3% formulation also had a higher efficacy compared to the vehicle. For this trial, the concentrations of 0.3%

and 1% are selected in the same manner as those in the phase 2 trial outside Japan (271-12-205).

[Treatment period]

Usually, topical drugs for AD are evaluated for their efficacy once in 1 to 2 weeks, and if no improvements are observed within a month, the patient is generally considered for referral to a more specialized institution.² Thus, Week 4 is established as an assessment point of the primary efficacy endpoint, and the treatment is also to be continued after Week 4 to assess the efficacy and safety thereafter. In the phase 2 trial in AD patients outside Japan (271-12-205), the incidence of success in IGA at Week 8 was 17.07%, 16.28%, and 10.81% in the 0.3% OPA-15406 group, the 1% OPA-15406 group, and the vehicle group, respectively. The incidence of success in IGA was higher in the 0.3% and 1% OPA-15406 groups than in the vehicle group, while no significant difference was observed. Also, no particular safety concerns were identified in the 0.3% and 1% formulations of OPA-15406. In this trial, the duration of treatment is established as 8 weeks to assess the efficacy and safety of the IMP in Japanese patients up to Week 8 and to compare the results with those of the ~~phase 2 trial outside Japan (271-12-205)~~

6.2 Treatment Area

The treatment area with the IMP is defined as follows.

- The treatment area selected at baseline examination will be affected area determined at baseline examination (see [7.2.1.7 “Affected BSA”](#)).
- After the baseline examination, when the affected area has expanded or a new affected area is detected, the expanded or newly affected area will also be included in the treatment area.
- Even when the affected area is relieved, the IMP administration should be continued there as the treatment area.

The investigator or subinvestigator will instruct the subject regarding the method of administration by specifying the treatment area (%) and the amount of administration (g) for each treatment area using the human body drawing (Appendix 5), and will give the human body drawing (copy) to the subject or the subject's legal guardian. The investigator or subinvestigator will record the treatment area (%) of the 4 body regions (face, neck, and head; upper limbs; trunk; and lower limbs) in the source document and case report form (CRF).

The method of IMP administration is specified in the separate procedure for IMP administration.

6.3 Prior and Concomitant Treatment

6.3.1 Prohibited Concomitant Drugs and Therapies

- 1) From 28 days prior to the baseline examination until the Week 8 examination, use of the following drugs and therapies is prohibited
 - Systemic corticosteroids, systemic immunomodulators, systemic antimetabolites, systemic retinoids, biologics
Intra-ocular, intra-nasal, and intra-auricular corticosteroids or inhaled corticosteroids may be considered if, in the opinion of the investigator or subinvestigator, their use will not impact assessment of the affected area.
 - Ultraviolet light A, narrowband ultraviolet B, ultraviolet light B
- 2) From 7 days prior to the baseline examination until the Week 8 examination, use of the following drugs and therapies is prohibited.
 - Topical corticosteroids, topical immunomodulators, topical retinoids, and topical antihistamine.
However, corticosteroids categorized as low or medium potency in the “Guidelines of care for management of atopic dermatitis, Section 2”² may be used up until the baseline examination if, in the opinion of the investigator or subinvestigator, their use is necessary, such as when the subjects have been using the corticosteroids prior to providing informed consent to participate in the trial and use of the corticosteroids will be tapered off and stopped during the screening period.
 - Systemic antihistamines, sodium cromoglicate, tranilast, suplatast tosilate
- 3) From the baseline examination until the Week 8 examination, use of the following drugs and products on the treatment area is prohibited.
 - All topical drugs (including ethical drugs, over-the-counter products, herbal medicine, quasi-drugs, and cosmetic products)
However, if cosmetic products were being used on the face, neck, and head prior to obtaining consent, their use may be continued only if the same products are used at the same frequency.

All other drugs and therapies not specified in the prohibited concomitant drugs and therapies are allowed to be used; however, any regimen or dose change or use of a new drug or therapy should be avoided as much as possible between the screening examination and the Week 8 examination. If any drug other than the IMP is used between 30 days before the screening examination and the Week 8 examination, the name of the drug, purpose of use, amount per dose, dose frequency, route of administration, and dates of start and end of administration will be recorded in the source

document and CRF, regardless of it being prohibited or allowed for concomitant use. If any concomitant therapy is given between 30 days before the screening examination and the Week 8 examination, regardless of it being prohibited or allowed for concomitant use, the name of the therapy, purpose of use, and the dates of the start and end of the therapy will be recorded in the source document and CRF.

[Rationale for prohibited concomitant drugs and therapies]

Due to a possible impact on the efficacy and safety assessments of the IMP.

6.4 Method of Minimizing or Avoiding Bias

This trial is a randomized, double-blind trial.

The IMP allocation manager will prepare a master “random allocation table” (hereinafter, “randomization table”) and conduct IMP coding according to the operating procedures for randomization. Also, the IMP allocation manager will prepare an emergency code list for use in emergencies such as the occurrence of a serious adverse event.

The investigator, subinvestigator, and subjects are blind to the IMP randomization code. Except for some designated personnel, the sponsor’s trial staff, including the personnel of contract research organizations, are also unable to access the IMP randomization code during the trial period.

Prior to the trial start and unblinding, the IMP allocation manager will confirm that the IMPs are indistinguishable. The randomization table is sealed by the IMP allocation manager just after completion of IMP randomization and it is kept under strict control until unblinding after fixation of all CRFs and the database.

The emergency code list will be kept under strict control by the registration system until the end of the trial. If a medical emergency occurs in a subject and knowledge of his or her IMP randomization code is considered important for treatment, the emergency code will be broken according to the “[8.2.4 Emergency Code Breaking \(Procedure for Unblinding During the Trial Period\)](#).”

When IMPs are recovered by the sponsor prior to unblinding, they are to be recovered sealed by the IMP allocation manager.

The subjects will be allocated to the 0.3% OPA-15406 group, the 1% OPA-15406 group, and the vehicle group in a ratio of 1:1:1 using dynamic allocation to ensure

balance within the trial sites and that of the baseline IGA (mild or moderate at the baseline examination).

The results of drug concentration measurements will not be revealed until unblinding at the end of the trial.

7 Observations/Examinations/Variables, Methods and Implementation Timings

7.1 Schedule and Procedures

The schedule of observations/examinations/evaluations is presented on pages 11 (Schedule of Observations/Examinations/Evaluations) to 14 (Schedule of Blood Sampling for Plasma Drug Concentration). Items that trial associates are capable of performing may be performed by trial associates under the supervision of the investigator.

7.1.1 Acquisition of Informed Consent

The investigator or subinvestigator will obtain written consent directly from subjects prior to the screening examination. If the subject is under 20 years old, written informed consent should be obtained from the subject and the subject's legal guardian. The investigator or subinvestigator will assign a subject identification code and subject number (3 digit number of site ID + S +5 digit serial number starting from 00001) to the subject providing consent.

7.1.2 Screening Examination (From the Day of Informed Consent to 2 Days Prior to the Baseline Examination)

After acquisition of informed consent, the investigator or subinvestigator will perform the following examinations, observations, and evaluations, and select subjects who meet the inclusion criteria and do not fall under any of the exclusion criteria.

- Subject demographics
- Physical examination
- Vital signs (including body weight)
- Clinical laboratory tests
- Pregnancy test (only for women of childbearing potential)
- 12-lead ECG
- IGA
- Affected BSA

- Adverse events
- Concomitant medications and therapies

Investigator or subinvestigator will record the results of the eligibility of subjects on the list of screened subjects and the list of enrolled subjects.

7.1.2.1 Subject Demographics

The investigator or subinvestigator will assess or measure the following items and record them in the source document and CRF.

- Date of informed consent
- Sex
- Date of birth
- Height (unit in cm: measurement indicated as an integer value; if measurement to one decimal place is possible, then the number is to be rounded to nearest integer value.)
- Complications
- Date of onset of AD
- Medical history (within 6 months prior to the date of informed consent)
- In- or outpatient status (outpatient)
- Subject number
- Country where the trial is conducted (Japan)
- Race (Asian)
- Ethnicity
- Possibility of pregnancy

7.1.3 Subject Registration

The investigator or subinvestigator will register all subjects in the Interactive Web Response System (IWRS).

7.1.4 Baseline Examination (2-30 Days After the Screening Examination)

The investigator or subinvestigator will perform the following examinations, observations, and evaluations, and record the results in the source document and CRF.

- Physical examination
- Vital signs (including body weight)
- Clinical laboratory tests (The screening examination results can be used within 7 days of the screening examination.)

- Pregnancy test (only for women of childbearing potential. The screening examination results can be used within 7 days of the screening examination.)
- 12-lead ECG (The screening examination results can be used within 7 days of the screening examination.)
- IGA
- EASI
- VAS for pruritus
- VRS for pruritus
- DLQI
- POEM
- Affected BSA
- Blood sampling for plasma drug concentration (to be conducted at specific trial sites)
- Severity of AD
- Adverse events
- Concomitant medications and therapies

The investigator or subinvestigator will select subjects who meet the inclusion criteria and do not meet any of the exclusion criteria based on results of the screening and baseline examinations. Also, the investigator or subinvestigator will record the results of the subject's eligibility on the list of screened subjects and the list of enrolled subjects.

7.1.5 Allocation of Investigational Medicinal Products to Subjects

The investigator or subinvestigator will enter the necessary information for the subject's eligibility in the IWRS. On the day of the baseline examination, the subjects confirmed to be registered in the IWRS will be allocated to the 0.3% OPA-15406 group, the 1% OPA-15406 group, or the vehicle group. The investigator or subinvestigator will confirm the allocation result and the amount of IMP to be prescribed for 2 weeks on the IWRS screen displaying the registration result, and prescribe the IMP. The weight of the dispensed IMP will be measured (unit in g; rounded to the one decimal place; same method for all subsequent IMP weight measurements hereinafter) The IMP administration will be started at the trial site after all baseline examinations are finished, and the time and date of administration will be recorded. The subjects will be instructed to visit the trial site without morning IMP administration on the day of their next visit.

**7.1.6 Baseline Examination (2 Hours, 4 Hours, and 8 Hours Postdose):
To be Conducted at Specific Trial Sites**

Application will be started within the trial site after all the baseline examinations are finished, and the source document and CRF will be recorded accordingly.

- Blood sampling for plasma drug concentration

7.1.7 Between the Day of Baseline Examination and the Day of Week 1 Examination

The investigator or subinvestigator will instruct the subject to evaluate the following item at 4 ± 2 hours, 8 ± 2 hours, and 12 ± 2 hours (if possible) after the first IMP administration on the day of the baseline examination, and then twice daily from the next day (before IMP administration in the morning and at night) up to the morning of the Week 1 examination (before administration) (up to the morning of Day 7 at the latest).

- VRS for pruritus

7.1.8 Week 1 Examination (± 2 Days)

The investigator or subinvestigator will perform the following examinations, observations, and evaluations, and record the results in the source document and CRF.

- Physical examination
- Vital signs (including body weight)
- IGA
- EASI
- VAS for pruritus
- DLQI
- POEM
- Affected BSA
- Blood sampling for plasma drug concentration measurement
- Adverse events
- Concomitant medications and therapies
- Status of IMP administration

The investigator or subinvestigator will determine the treatment area (%) and enter it in the IWRS. Also, the investigator or subinvestigator will confirm the subject's

allocation status on the IWRS screen and, if necessary, prescribe additional IMP. When the IMP is additionally prescribed, the weight of dispensed IMP will be measured.

7.1.9 Week 2 Examination (± 3 Days)

The investigator or subinvestigator will perform the following examinations, observations, and evaluations, and record the results in the source document and CRF.

- Physical examination
- Vital signs (including body weight)
- IGA
- EASI
- VAS for pruritus
- DLQI
- POEM
- Affected BSA
- Adverse events
- Concomitant medications and therapies
- Status of IMP administration

The investigator or subinvestigator will collect the IMP and measure the weight of the collected IMP. The investigator or subinvestigator will determine the treatment area (%) and enter it in the IWRS. The investigator or subinvestigator will confirm the amount of IMP to be prescribed for the next 2 weeks and prescribe it. The weight of the dispensed IMP will be measured. The subjects will be instructed to visit the trial site without morning IMP administration on the day of the next visit.

7.1.10 Week 4 Examination (± 3 Days)

The investigator or subinvestigator will perform the following examinations, observations, and evaluations, and record the results in the source document and CRF.

- Physical examination
- Vital signs (including body weight)
- Clinical laboratory tests
- Pregnancy test (only for women of childbearing potential)
- 12-lead ECG
- IGA
- EASI
- VAS for pruritus
- DLQI

- POEM
- Affected BSA
- Blood sampling for plasma drug concentration measurement
- Adverse events
- Concomitant medications and therapies
- Status of IMP administration

The investigator or subinvestigator will collect the IMP and measure the weight of the collected IMP. The investigator or subinvestigator will determine the treatment area (%) and enter it in the IWRS. The investigator or subinvestigator will confirm the amount of IMP to be prescribed for the next 2 weeks and prescribe it. The weight of the dispensed IMP will be measured.

7.1.11 Week 4 Examination (2 Hours, 4 Hours, and 8 Hours Postdose): To Be Conducted at Specific Trial Sites)

Application will be started within the trial site after all Week 4 examinations are finished, and the source document and CRF will be recorded accordingly.

- Blood sampling for plasma drug concentration

7.1.12 Week 6 Examination (± 3 Days)

The investigator or subinvestigator will perform the following examinations, observations, and evaluations, and record the results in the source document and CRF.

- Physical examination
- Vital signs (including body weight)
- IGA
- EASI
- VAS for pruritus
- DLQI
- POEM
- Affected BSA
- Adverse events
- Concomitant medications and therapies
- Status of IMP administration

The investigator or subinvestigator will collect the IMP and measure the weight of the collected IMP. The investigator or subinvestigator will determine the treatment area (%) and enter it in the IWRS. The investigator or subinvestigator will confirm the

amount of IMP to be prescribed for the next 2 weeks and prescribe it. The weight of the dispensed IMP will be measured. The subjects will be instructed to visit the trial site without morning IMP administration on the day of the next visit.

7.1.13 Week 8 Examination (± 3 Days) or Withdrawal Examination

The investigator or subinvestigator will perform the following examinations, observations, and evaluations, and record the results in the source document and CRF. Withdrawal examinations should be conducted if at all possible.

- Physical examination
- Vital signs (including body weight)
- Clinical laboratory tests
- Pregnancy test (only for women of childbearing potential)
- 12-lead ECG
- IGA
- EASI
- VAS for pruritus
- DLQI
- POEM
- Affected BSA
- Blood sampling for plasma drug concentration measurement
- Adverse events
- Concomitant medications and therapies
- Status of IMP administration

The investigator or subinvestigator will collect the IMP and measure the weight of the collected IMP.

7.1.14 Examination 2 Weeks After Last IMP Administration (± 7 Days)

The investigator or subinvestigator will perform the following examinations, observations, and evaluations, and record the results in the source document and CRF.

- Physical examination
- Adverse events

7.1.15 Unscheduled Visits

The investigator or subinvestigator will instruct the subjects to visit the trial site if the area of affected BSA markedly enlarges. The investigator or subinvestigator will

perform the following examinations, observations and evaluations, and record the results in the source document and CRF.

- Affected BSA
- Adverse events
- Concomitant medications and therapies

The following examinations may be conducted as necessary:

- Physical examinations
- Vital signs (including body weight)
- 12-lead ECG
- Clinical laboratory values
- Pregnancy test

The investigator or subinvestigator will determine the treatment area (%) and enter it in the IWRS. Also, the investigator or subinvestigator will confirm the subject's allocation status on the IWRS screen and, if necessary, prescribe additional IMP. When the IMP is additionally prescribed, the weight of dispensed IMP will be measured.

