3.3.1.2 Secondary Variable(s)

- 1) Incidence of success in IGA at Week 1 and Week 8
- 2) Change from baseline in IGA at Week 1, Week 4, and Week 8
- 3) Change from baseline in the total score of Eczema Area and Severity Index (EASI) and each symptom score at Week 1, Week 4, and Week 8

- 4) Change from baseline in Visual Analogue Scale (VAS) for pruritus at Week 1, Week 4, and Week 8
- 5) Change from baseline in Verbal Rating Scale (VRS) for pruritus up to Day 7
- 6) Change from baseline in the total score of Dermatology Life Quality Index (DLQI) at Week 1, Week 4, and Week 8
- 7) Change from baseline in the total score of Patient-Oriented Eczema Measure (POEM) at Week 1, Week 4, and Week 8
- 8) Change from baseline in the total affected BSA (%) at Week 1, Week 4, and Week 8
- 9) Time to response in IGA and VRS

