## 6.4 Study Week Windows

The definitions of timepoints for analysis are described in Table 6.4-1 and Table 6.4-2. Timepoints, including unscheduled visits and visit at discontinuation, will be determined based on the number of days from the start of IMP administration. However, for Verbal Rating Scale (VRS), the timepoint will be determined based on the amount of time that has elapsed from the start of IMP administration. For efficacy variables, the data obtained between the day of the start of IMP administration and 7 days after the last IMP administration will be used in analyses. If multiple data exist within the allowable window of the timepoint, the data obtained last will be used for analyses. Data for the Last Visit will be defined as the last data obtained between the day of the start of IMP administration and 7 days after the last IMP administration (including data obtained at discontinuation) for efficacy variables or as the last data obtained after the start of the IMP administration for safety variables.

In analyses, baseline data will be defined as data obtained on the day or at the date and time before and nearest to the start of IMP administration, including the screening data.

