**Table 6.4-1 Timepoints and Allowable Windows for Efficacy Variables (Except VRS) and Safety Variables**

Timepoint	Study Day	Allowable Window (Days After the Start of IMP Administration)		
Week 1	8	1	-	10
Week 2	15	11	-	21
Week 4	29	22	-	35
Week 6	43	36	-	48
Week 8	57	49	-	73

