#### **9.2.8      Change From Baseline in Overall Percentage Affected BSA at Week 1, Week 4, and Week 8**

The change from baseline in overall percentage affected BSA will be analyzed in the same manner as that in the overall EASI score or each EASI symptom score.

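### A worsening-triggered affected-BSA value from an unscheduled visit can replace the scheduled value in the Week 1 and Week 4 windows; scheduled values should take precedence

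*Protocol*

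**What the plan says.** **Trigger and content of the visit.** Protocol 7.1.15 tells the investigator to "instruct the subjects to visit the trial site if the area of affected BSA markedly enlarges". Affected BSA, adverse events and concomitant treatment are recorded. A second list, introduced by "The following examinations may be conducted as necessary", contains only safety items. IGA, EASI, pruritus VAS, DLQI and POEM are in neither list, although all five are measured at every scheduled visit from Week 1 to Week 8 (Protocol 7.1.8 to 7.1.13).

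**Entry into the analysis.** SAP 6.4 states: "Timepoints, including unscheduled visits and visit at discontinuation, will be determined based on the number of days from the start of IMP administration". It then sets the tie rule: "If multiple data exist within the allowable window of the timepoint, the data obtained last will be used for analyses". On the period that counts for efficacy it says: "the data obtained between the day of the start of IMP administration and 7 days after the last IMP administration will be used in analyses". Nothing gives a scheduled visit precedence or prefers the value nearest the target day.

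**The endpoint.** Protocol 3.3.1.2 lists as a secondary variable: "Change from baseline in the total affected BSA (%) at Week 1, Week 4, and Week 8". SAP 9.2.8 says: "The change from baseline in overall percentage affected BSA will be analyzed in the same manner as that in the overall EASI score". By reference to SAP 9.2.3 that means MMRM on observed cases, ANCOVA on observed-case and LOCF data, and descriptive summaries, with Weeks 2 and 6 also reported. Unscheduled values are not excepted.

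**The concern.** The sampling depends on the outcome. A subject whose affected area grows markedly is called in and measured again, and that reading can overwrite a valid one taken on schedule. A subject whose area shrinks gets no extra visit. The mean at a nominal timepoint is then a mixture of on-schedule readings and readings that exist because BSA got worse.

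Two things are at stake. First, if enlargement visits differ in frequency or size between arms, the BSA contrast moves against the arm with more of them; in a vehicle-controlled trial that may well be vehicle. Second, BSA and EASI reported for the same timepoint can come from different days, because EASI is not listed for these visits and keeps its scheduled value. The two would then describe different disease states under one label.

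**Working it through.** The plan gives no figure for this point. Its sample-size calculation concerns the IGA endpoint and does not bear on it. The check is a count of days followed by an illustration of size.

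**Step 1: days on which an unscheduled value wins.** Target days and windows come from SAP Table 6.4-1. Scheduled visits are assumed to fall on the target day, and days are counted from Day 2 to Day 56.

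| Timepoint | Target day | Window | Days after the scheduled visit, in window | Non-visit days in window |
|---|---|---|---|---|
| Week 1 | 8 | 1-10 | 9-10 (2) | 2-7, 9-10 (8) |
| Week 2 | 15 | 11-21 | 16-21 (6) | 11-14, 16-21 (10) |
| Week 4 | 29 | 22-35 | 30-35 (6) | 22-28, 30-35 (13) |
| Week 6 | 43 | 36-48 | 44-48 (5) | 36-42, 44-48 (12) |
| Week 8 | 57 | 49-73 | none up to Day 56 | 49-56 (8) |

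- All windows: 2 + 6 + 6 + 5 = 19 of 8 + 10 + 13 + 12 + 8 = 51 days, or 37%.
- Named timepoints (Weeks 1 and 4): 2 + 6 = 8 of 51, or 16%.
- Weeks 2 and 6, which feed the MMRM and are also reported: 6 + 5 = 11 days.
- On the other 51 - 19 = 32 days, the later scheduled value overrides the unscheduled one unless that visit is missed.

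**Step 2: visit tolerance.** The Week 1 visit may move by 2 days (Protocol 7.1.8). A visit on Day 6 leaves Days 7-10 (4 days), and a visit on Day 10 leaves none. The Week 4 visit may move by 3 days (Protocol 7.1.10). A visit on Day 26 leaves Days 27-35 (9 days), and one on Day 32 leaves Days 33-35 (3 days).

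**Step 3: Week 8.** The Week 8 examination is normally the last BSA reading, and the examination two weeks after the last dose does not include BSA (Protocol 7.1.14). A later value could enter only from an unscheduled visit within 7 days of the last dose.

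**Step 4: size, on assumed inputs.** Let f be the share of an arm with one enlargement visit in the window. Let d be displacing days divided by non-visit days in that window, taking the visit as equally likely on each. Let e be the mean excess over the scheduled reading in BSA percentage points, taken as equal in the arms. Then:

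shift in the contrast = (f_vehicle - f_active) x d x e

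With f = 10% on vehicle and 4% on active, and e = 10:

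- Week 1: 0.06 x 2/8 x 10 = 0.15 points.
- Week 4: 0.06 x 6/13 x 10 = 0.28 points.
- Week 8: about 0.

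The range can be set out directly from the share of subjects whose scheduled value is displaced (f x d), with e from 5 to 15 points:

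| Displaced, active | Displaced, vehicle | Shift in contrast (points) |
|---|---|---|
| 5% | 5% | 0 |
| 2% | 5% | 0.15 to 0.45 |
| 5% | 15% | 0.5 to 1.5 |
| 5% | 20% | 0.75 to 2.25 |

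With equal shares and equal excess the contrast does not move, although each arm's mean is still raised.

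**The case against.** A BSA reading during a flare is a genuine on-treatment observation. If vehicle subjects flare more, part of any shift is treatment effect, and only the excess over the on-schedule contrast is distortion. Every arm is measured at five scheduled visits whatever the direction of change, so most unscheduled readings are superseded. A subject whose treatment area passes 40% of BSA is withdrawn (Protocol 9.2) and should have a full withdrawal examination including IGA and EASI (Protocol 7.1.13), so the BSA-only asymmetry is not universal. BSA is one of nine secondary variables, analysed for reference without multiplicity adjustment (Protocol 11.3.7, SAP 6.6.1).

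All of this stands, and it limits the importance of the point. It does not remove the mechanism: a reading from Day 33 taken because of enlargement does not estimate status at the scheduled Week 4 visit when a valid reading from that visit exists.

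A reader might go further in three ways that the documents do not support:

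- **That about 40% of unscheduled readings corrupt the endpoint.** Counting Days 2-48 gives 19 of 47, but 11 of those days belong to Weeks 2 and 6, the denominator includes four scheduled visit days, and the count leaves out the protected run-up to Week 8.
- **That the analysis is known to favour the drug.** This needs more frequent or larger enlargement readings on vehicle, and no such data are given.
- **That all unscheduled BSA values should be dropped.** This would discard the only reading in a window when the scheduled visit was missed. LOCF would then carry an earlier, better value for a subject known to have worsened.

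**Conclusion.** The route into the endpoint is explicit in the documents, and the point holds as a minor one. A worsening-triggered BSA value can displace a valid scheduled value at two of the three named timepoints, on 8 of 51 non-visit days (16%) with on-target visits. Week 8 is largely protected, and the primary IGA endpoint is not affected because IGA is not listed for these visits. The direction of any shift depends on how enlargement visits differ between arms. The illustrative 0.15 points at Week 1 and 0.28 points at Week 4 rest wholly on assumed visit rates, an assumed excess and an even spread of visit days.

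**What to change.** In SAP 6.4, add for affected BSA: within a window, the value from the scheduled visit or the withdrawal examination takes precedence, and an unscheduled value is used only when neither exists in that window. If both a scheduled and a withdrawal value are present, the existing last-value rule can decide between them. List all unscheduled BSA values, and report by arm the number of subjects with an enlargement visit.

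With on-target visits this cuts displacing days from 2 to 0 at Week 1 and from 6 to 0 at Week 4, and any shift in the contrast by this route becomes zero. Sample size, visits and data collection are unchanged. The cost is a sentence or two in the SAP before database lock, a record-selection rule, a listing and a count.

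The downside is that a worsening later in the same window no longer enters that timepoint's mean, though it stays visible in the listing and counts. The SAP should also say which value LOCF carries when such a subject then leaves without a withdrawal examination.
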